6.4 Reporting of serious adverse events

All SAEs have to be reported, whether or not considered causally related to the IP, or to the study procedure(s). All SAEs will be recorded in the CRF.

If any SAE occurs in the course of the study, then Investigators or other site personnel will inform the appropriate AstraZeneca representatives within 1 day, i.e., immediately but **no later than 24 hours** from when he or she becomes aware of it.

The designated AstraZeneca representative will work with the Investigator to ensure that all the necessary information is provided to the AstraZeneca Subject Safety data entry site **within 1 calendar day** of initial receipt for fatal and life threatening events **and within 5 calendar days** of initial receipt for all other SAEs.

For fatal or life-threatening AEs where important or relevant information is missing, active follow-up will be undertaken immediately. Investigators or other site personnel will inform AstraZeneca representatives of any follow-up information on a previously reported SAE **within 1 calendar day**, i.e., immediately but **no later than 24 hours** from when he or she becomes aware of it.

Once the Investigators or other site personnel indicate an AE is serious in the WBDC system, an automated email alert will be sent to the designated AstraZeneca representative.

If the WBDC system is not available, then the Investigator or other study site personnel is to report a SAE to the appropriate AstraZeneca representative by telephone.

The AstraZeneca representative will advise the Investigator/study site personnel how to proceed.

The reference document for definition of expectedness/listedness is the IB for the AstraZeneca drug.

6.5 Overdose

- An overdose with associated AEs will be recorded as the AE diagnosis/symptoms on the relevant AE modules in the CRF and on the Overdose CRF module.
- An overdose without associated symptoms will be reported on the Overdose CRF module only.

If an overdose on an AstraZeneca study drug occurs in the course of the study, then the Investigator or other site personnel will inform appropriate AstraZeneca representatives immediately but **no later than 24 hours** from when he or she becomes aware of it.

The designated AstraZeneca representative will work with the Investigator to ensure that all relevant information is provided to the AstraZeneca Subject Safety data entry site.

For overdoses associated with a SAE, the standard reporting timelines apply, see Section 6.4. For other overdoses, reporting must occur within 30 days.

6.6 Pregnancy

All pregnancies and outcomes of pregnancy should be reported to AstraZeneca.

6.6.1 Maternal exposure

If a subject becomes pregnant during the course of the study IP should be discontinued immediately.

Pregnancy itself is not regarded as an AE unless there is a suspicion that the IP under study may have interfered with the effectiveness of a contraceptive medication. Congenital abnormalities/birth defects and spontaneous miscarriages should be reported and handled as SAEs. Elective abortions without complications should not be handled as AEs. The outcome of all pregnancies (spontaneous miscarriage, elective termination, ectopic pregnancy, normal birth or congenital abnormality) should be followed up and documented even if the subject was discontinued from the study.

If any pregnancy occurs in the course of the study, then the Investigator or other site personnel will inform the appropriate AstraZeneca representatives within 1 day, i.e., immediately but **no later than 24 hours** from when he or she becomes aware of it.

The designated AstraZeneca representative works with the Investigator to ensure that all relevant information is provided to the AstraZeneca Subject Safety data entry site within 1 or 5 calendar days for SAEs (see Section 6.4) and within 30 days for all other pregnancies.

The same timelines apply when outcome information is available.

The pregnancy (PREGREP) module in the CRF will be used to report the pregnancy and the pregnancy outcome (PREGOUT) module will be used to report the outcome of the pregnancy.

6.6.2 Paternal exposure

Male subjects should refrain from fathering a child or donating sperm during the study and for 16 weeks (5 half-lives) following the last dose.

Pregnancy of the subject's partners will not be considered an AE. However, the outcome of all pregnancies (spontaneous miscarriage, elective termination, ectopic pregnancy, normal birth, or congenital abnormality) should be followed up and documented for conceptions

occurring from the date of the first administration of IP until 16 weeks (5 half-lives) after the last administration of IP.

7. INVESTIGATIONAL PRODUCT AND OTHER TREATMENTS

7.1 Identity of investigational product(s)

All investigational products will be manufactured in accordance with Good Manufacturing Practice (GMP).

Benralizumab and placebo administered in the study will be a clear to opalescent, colourless to yellow solution.

Table 4 Identity of investigational product

Investigational product	Dosage form and strength	Manufacturer
Benralizumab	30 mg/mL solution for injection in accessorized pre-filled syringe, 1mL fill volume	MedImmune
Placebo	Matching placebo solution for injection in accessorized pre-filled syringe, 1mL fill volume	MedImmune

7.2 Dose and treatment regimens

The IP will be administered at the study centre on treatment visits and within visit windows as specified in [Table 2](#).

Before IP administration

Prior to each IP administration:

Investigator/authorized delegate will assess injection site as per standards of medical care

For WOCBP urine pregnancy test will be done; IP will be administered only when the result of the test is negative (see Section [5.2.1](#))

IP administration

The IP will be administered by the Investigator/authorized delegate. It is suggested that the site of injection of the IP is rotated such that the patient receives IP at a different anatomical site (see [Figure 2](#)) at each treatment visit. The injection site must be recorded in the source documents and the eCRF at each treatment visit.

Figure 2 **Injection sites and rotation scheme**

Further details on IP administration are provided in the IP Handling Instruction. IP administration must be carried out in line with the Instruction.

After IP administration

After IP administration the subject should be observed for a minimum of 2 hours for the appearance of any acute drug reactions.

Conditions requiring IP administration rescheduling

If any of the following should occur, the investigator should reschedule the visit and the IP should not be administered until the rescheduled visit:

- The subject has an intercurrent illness, that in the opinion of the investigator may compromise the safety of the subject in the study (eg, viral illnesses)
- The subject is febrile ($\geq 38^{\circ}\text{C}$; $\geq 100.4^{\circ}\text{F}$) within 72 hours prior to IP administration

7.3 Management of IP related reactions

Appropriate drugs, such as epinephrine, H1 and H2 antihistamines, and corticosteroids, as well as medical equipment to treat acute anaphylactic reactions must be immediately available. Study personnel must be trained to recognize and treat anaphylaxis ([Lieberman et al 2010](#)). Details on anaphylaxis management are provided in [Appendix D](#).

Anaphylaxis will be defined as a serious reaction that is rapid in onset and may cause death ([Simpson et al 2006](#)). Anaphylaxis typically manifests as 1 of 3 clinical scenarios:

1. The acute onset of a reaction (minutes to hours) with involvement of the skin, mucosal tissue, or both, and at least one of the following: a) respiratory compromise; or b) reduced blood pressure or symptoms of end-organ dysfunction

2. Two or more of the following that occur rapidly after exposure: involvement of the skin/mucosal tissue, respiratory compromise, reduced blood pressure or associated symptoms, and/or persistent gastrointestinal symptoms
3. Reduced blood pressure after exposure

Subjects will have had a pre-assessment (ie, vital signs) prior to IP administration and should be observed after IP administration for a minimum of 2 hours for the appearance of any acute drug reactions.

Serum tryptase or other blood or urine testing relevant to the diagnosis of anaphylaxis may be obtained at a local lab at the discretion of the investigator.

7.4 Labelling

Labelling of the IP will be carried out by AstraZeneca or designee in accordance with current Good Manufacturing Practice (GMP) and regulatory requirements of each country participating in the study. The labels will be translated into local languages where applicable.

The labels will include the following information:

- Study code
- Investigational product/study drug dosage form, route of administration, and quantity of dosage units
- Kit ID
- P Lot ID
- Expiry date
- Investigator name (to be written on the label)
- E-code (to be written on the label)
- Sponsor name
- Directions for use
- Storage conditions
- Standard statements required by Regulatory Authorities
- Sponsor name and contact details

7.5 Storage

Benralizumab/placebo is to be stored at the study centre in a secured facility with limited access and controlled temperature. The temperature should be monitored on a daily basis and documented in the temperature monitoring log.

The IP must be kept in the original outer container and under conditions specified on the label (between 2–8°C (36–46°F), protected from the light).

In the following cases:

- Temperature excursion upon receipt or during storage at the study
- Damaged kit upon receipt
- Damaged syringe/cartridge

The centre staff should not use affected IP and should immediately contact an AstraZeneca representative for further guidance. Damaged IP should be documented via IWRS/IVRS (please refer to IWRS/IVRS manual for further details).

7.6 Compliance

The administration of all study drugs (including investigational products) should be recorded in the appropriate sections of the eCRF.

The IP will be administered at the study centre on treatment visits and within visit windows as specified in [Table 2](#). If 1 dose of the IP is missed during course of the study the subject should be discontinued; please refer to [Section 3.9](#).

7.7 Accountability

The study drug provided for this study will be used only as directed in the study protocol.

The study personnel will account for all study drugs dispensed to the patient.

The monitor will account for all study drugs received at the centre, unused study drugs, and for appropriate destruction. Certificates of delivery, destruction, and/or return should be signed.

In the case of a malfunctioning accessorized prefilled syringe (APFS), the centre should contact the study monitor to initiate a product complaint process according to applicable guidelines.

7.8 Concomitant and other treatments

The Informed Consent form must be signed before conducting any study-related procedures, e.g. discontinuation of pre-study treatment.

During the study, all subjects should have access to a SABA.

Salbutamol pMDI, inhaled corticosteroid, and prednisolone will be provided in connection with study assessments, when/if applicable as per the [REDACTED] SOPs.

Restricted medication during the study is shown in [Table 5](#).

Table 5 Restricted Medications

Restricted Medication prior to Visits 1a-17	Time limits prior to Visits 1a-17
Aspirin prn (all doses)	7 days
NSAIDs	72 hours
Ephedrine-containing drugs	24 hours
Inhaled/oral short-acting β 2-agonists (SABA)	8 hours
Short-acting anti-histamines ^a	3 days
Intermediate anti-histamines ^a	7 days
Long-acting anti-histamines ^a	9 days
Xanthine (tea, coffee, chocolate) ^b	4 hours

^a Prior to skin prick test and inhaled allergen testing only. Please refer to [REDACTED] SOPs for further guidance.

^b Applicable only to visits where spirometry will be conducted.

Medication not allowed during the study, from Visit 1a to end of Visit 17 are shown in [Table 6](#).

Table 6 Non-allowed medication

Non-allowed medication during the study (Visits 1a-17)	Time limit prior to Visit 1a
Inhaled ^a and nasal ^b steroids	4 weeks
Oral, rectal, parenteral (including periarticular injections) steroids ^c	3 months
Topical GCS for dermal use, group II – IV ^d	from Visit 2
Chronic use of anticoagulants and antiplatelet medication	4 weeks
Herbal remedies for the treatment of allergic, inflammatory, or respiratory diseases	30 days
Inhaled disodium cromoglycate and inhaled nedocromil sodium	4 weeks
Inhaled/oral long-acting β 2-agonists (LABA)	14 days
Leukotriene antagonists and 5-Lipoxygenase Inhibitors	14 days

Non-allowed medication during the study (Visits 1a-17)	Time limit prior to Visit 1a
Inhaled short-acting anticholinergics	8 hours
Inhaled long-acting anticholinergics	14 days
Theophylline	4 weeks
Betablockers including eyedrops	from Visit 2
Macrolide antibiotics	from Visit 2
Immunosuppressives ^e	3 months
Immunoglobulins and blood products	30 days
Allergen immunotherapy	4 months
Any marketed or investigational biologic ^e	4 months or 5 half-lives (whichever is longer)
Live attenuated vaccines ^e	30 days
Any investigational non-biologic	30 days or 5 half-lives (whichever is longer)

^a Use of inhaled steroids is prohibited during the study (please see section 3.8 for further details). Inhaled ICS may be used acutely after allergen challenge or to stabilize asthma during the study if needed, provided dosing is acute (3-5 days maximum) and washout (1 week) is applied before study visits.

^b Use of nasal steroids is prohibited during the study (please see section 3.8 for further details). If there is a need for acute use of nasal steroids a 12 hour washout period is required prior to any study related procedures.

^c Use of systemic steroids is prohibited during the study (please see section 3.8 for further details). Systemic steroids may be used acutely after allergen challenge or to stabilize asthma during the study if needed, provided a washout (1 week) is applied before study visits.

^d Topical GCS group I are allowed on areas up to the size of the subject's palm.

^e Please refer to section 3.8 for further details.

7.8.1 Other concomitant treatment

Medications other than those described above which are considered necessary for the safety and well-being of the subject, may be given at the discretion of the Investigator and recorded in the appropriate sections of the Case Report Form.

8. STATISTICAL ANALYSES BY ASTRAZENECA

8.1 Statistical considerations

- All personnel involved with the analysis of the study will remain blinded until database lock and protocol violators identified.
- Analyses will be performed by AstraZeneca or its representatives.
- Full details of the analyses for this study will be detailed in the Statistical Analysis Plan (SAP) which will be completed prior to unblinding of the data.

8.2 Sample size estimate

It is expected that approximately 38 subjects in total and 19 subjects in each treatment group are needed for this study. This is based on two primary endpoints the allergen induced change in percentage of eosinophils in induced sputum at 7-hr post allergen challenge during Allergen Challenge 1, and the maximum percent decrease in FEV₁ in late asthmatic response (LAR_{3-7 hr}), also during Allergen Challenge 1. These endpoints will be tested using step down approach (first assessing the effect on percentage of eosinophils in sputum) as described in section 8.5.

For the percent eosinophils in induced sputum, it is assumed the mean of Placebo group and the standard deviation [SD] are similar to sputum eosinophil data from a previously conducted study (mean of 20.8, and a SD of 17.3 at 7-hr post challenge in Placebo group). A sample size of approximately 19 subjects per treatment group (38 total) will be needed to achieve 80% power of detecting an 80% reduction in the Benralizumab group versus Placebo, assuming mean of 20.8 in Placebo group, and a SD of 17.3. This calculation assumed a two-sided 5% alpha level.

For the maximum percent decrease in FEV₁ LAR_{3-7hr}, a sample size of approximately 19 subjects per treatment group (38 total) will be needed to achieve 80% power of detecting a 11% absolute difference between Benralizumab group and Placebo, assuming a SD of 12% (similar to the variability estimated in [Gauvreau et al 2014](#)). This calculation assumed a two-sided 5% alpha level.

Based on previous studies with bone marrow aspirate collections, it is estimated that approximately 22 subjects are required to be able to detect meaningful differences between placebo and active treatment.

Although formal powering has been used to estimate the sample size required it is expected to be sufficient for all endpoints using an estimation type approach which has been used for most studies of this type.

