This submission document contains confidential commercial information, disclosure of which is prohibited without providing advance notice to AstraZeneca and opportunity to object.

This Clinical Study Protocol has been subject to a peer review according to AstraZeneca Standard procedures. The clinical study protocol is publicly registered and the results are disclosed and/or published according to the AstraZeneca Global Policy on Bioethics and in compliance with prevailing laws and regulations.

PROTOCOL SYNOPSIS

A Double-Blind, Randomized, Parallel Group, Placebo-Controlled Multi-Centre Study to Evaluate the Effect of Benralizumab on Allergen-Induced Inflammation in Mild, Atopic Asthmatics

National Co-ordinating Investigator

[REDACTED]

Study site(s) and number of subjects planned

The study will include approximately 38 randomised patients, recruited at 6 centres [REDACTED] in Canada.

Study period	Phase of development	
Estimated date of first subject enrolled	Q3 2016	3
Estimated date of last subject completed	Q4 2018	3

Study design

This randomized, double-blind, parallel group, placebo-controlled study will evaluate the effect of a fixed 30 mg dose of benralizumab administered subcutaneously every 4 weeks on allergen-induced inflammation in subjects with mild atopic asthma challenged with an inhaled allergen.

Subjects who meet the eligibility criteria will be randomized to receive 3 subcutaneous (SC) doses of benralizumab 30 mg or placebo (1:1).

Following the third dose of study treatment subjects will return to the clinic for the two allergen challenge periods. The first allergen challenge will assess effects of benralizumab on allergen-induced eosinophils in induced sputum and the late asthmatic response (LAR). The second allergen challenge will assess effects of benralizumab on allergen-induced eosinophils and basophils in lung tissue. Only clinical sites participating in bronchial biopsy collections

will participate in the second allergen challenge. Subjects will return to the clinic 8 weeks and 12 weeks following the last dose of benralizumab for End-of-Treatment (EOT) and follow-up assessments, respectively.

Objectives

(a) Primary Objectives

Objective	Outcome Measure
To evaluate the effect of benralizumab on allergen-induced increases in eosinophils in induced sputum	Change in percent of eosinophils in sputum 7 hours post allergen challenge

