1.4 Study Design

This randomized, double-blind, parallel group, placebo-controlled study will evaluate the effect of a fixed 30 mg dose of benralizumab administered SC every 4 weeks for 3 doses on allergen-induced inflammation in subjects with mild atopic asthma challenged with an inhaled allergen.

Approximately 38 non-smoking men and women (18 – 65 years of age) corticosteroid-free (oral and inhaled) mild, atopic asthmatics who have demonstrated a dual (early and late) asthmatic response to inhaled allergen challenge at screening will be recruited to complete the study.

This study will include 6 centres in [REDACTED] Canada. All centres will participate in the characterization of the early and late asthmatic response and induced sputum collections. A subset of 5 centres will conduct the endobronchial biopsy collections, and bone marrow aspirates will be conducted at one centre only.

After enrolment and confirmation of entry criteria, subjects will enter a 4 week run-in period during which their suitability for randomization will be confirmed and to allow resolution of airway inflammation induced from the allergen challenge screening assessments. Subjects

who meet all the eligibility criteria will return to the clinic for collection of tissue samples according to the participation of the study site (sputum, bone marrow aspirates, lung biopsies and blood) for assessment of baseline inflammation. This will be conducted at 2 visits over a 3 day period.

[figure not shown]
Subjects will then be randomized to receive either benralizumab 30 mg SC or matching placebo (1:1). Subjects will receive 2 additional doses of study treatment every 4 weeks for a total of 3 doses.

Twenty eight days following the first dose, subjects will return to the clinic for assessment of dosing effects on airway hyperresponsiveness (MCh PC20) and collection of a blood sample for eosinophil and serum biomarkers measurements and a sputum sample for eosinophil and biomarker measurements.

Twenty eight days following the second dose, subjects will return to the clinic for assessment of dosing effects on baseline inflammation in the lung biopsies (only sites participating in the bronchial biopsy collections) and collection of a blood sample (all sites) for blood eosinophil measurements. Subjects will then receive a third dose of study treatment and return to the clinic no less than 7 days later for the first allergen challenge period.

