There are two primary endpoints, the allergen induced change in percentage of eosinophils in sputum 7-hr post allergen challenge and maximum percent decrease in FEV₁ in the late asthmatic response on Visit 11. These endpoints will be tested using the following hierarchical fixed-sequence approach in order to control the overall type I error rate at the 0.05 level:

Step 1 first perform the test on allergen induced change in percentage of eosinophils in sputum 7-hr post allergen challenge. If the p-value is ≤ 0.05 , then proceed with Step 2. Otherwise, neither of the two hypothesis will be rejected.

Step 2 perform the test on maximum percent decrease in FEV₁ in the late asthmatic response on Visit 11, at alpha level of 0.05.

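### The 80% power for the late asthmatic response is a per-endpoint figure; under the fixed test sequence the planned chance of declaring that effect is about 65% to 71%

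*Protocol*

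**What the plan says.** Section 8.2 powers the two primary endpoints one at a time.

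- **Sputum eosinophils at 7 hours:** 19 per group for 80% power of "detecting an 80% reduction in the Benralizumab group versus Placebo, assuming mean of 20.8 in Placebo group, and a SD of 17.3".
- **LAR (maximum percent fall in FEV1 at 3 to 7 hours):** about 19 per group "will be needed to achieve 80% power of detecting a 11% absolute difference between Benralizumab group and Placebo", "assuming a SD of 12" percent.

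For each endpoint it adds: "This calculation assumed a two-sided 5% alpha level". The section mentions that the endpoints are tested step-down with eosinophils first, but gives no power for passing both steps, no correlation between the endpoints and no allowance for loss of data.

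The testing strategy in section 8.5 goes on to LAR only if the eosinophil p-value is at most 0.05. If it is not, the rule reads: "Otherwise, neither of the two hypothesis will be rejected".

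On the meaning of 38, the synopsis states: "The study will include approximately 38 randomised patients". Section 1.4 gives the same number as subjects who "will be recruited to complete the study". Section 8.2 says only that 38 are needed. Section 3.10.2 permits, but does not require, replacement of withdrawn subjects.

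**The concern.** Under the fixed sequence, a significant LAR result requires two events: the eosinophil test succeeds and the LAR test succeeds. The probability of both is lower than the probability of the second alone unless the two tests are almost completely dependent. Section 8.2 quotes only the second. LAR is one of the two primary objectives, and attenuation of LAR is the hypothesis put forward in section 1.1. Anyone using section 8.2 to judge how likely the trial is to support that hypothesis formally would therefore take 80%, when the design's own rule gives less.

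The unclear meaning of 38 bears on the same figure. The power calculation needs 19 subjects per arm with Visit 11 data, and the protocol has routes by which a randomised subject provides none:

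- Under sections 3.9 and 7.6, a subject who misses one dose is discontinued from study drug, and section 3.9 then specifies only the discontinuation and follow-up visits.
- Under section 4.2.2.2, if FEV1 is too low, procedures cannot continue and rescheduling is exhausted, biopsy subjects pass over the first allergen challenge and go on to the second, while the others are withdrawn.
- The biopsy subjects in that situation remain in the study, so they are not withdrawn subjects whom section 3.10.2 would allow to be replaced. Five of the six centres take biopsies.

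**Working it through.** **Inputs (section 8.2).** Eosinophils: difference 0.80 × 20.8 = 16.64, SD 17.3. LAR: difference 11, SD 12. Two-sided alpha 0.05 for each, 19 per arm, 1:1.

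**Step 1: reproduce the plan's figure.** Normal approximation, n per arm = 2(1.960 + 0.842)² (SD/difference)².

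- LAR: 2 × 7.849 × (12/11)² = 18.7, so 19.
- Eosinophils: 2 × 7.849 × (17.3/16.64)² = 17.0, so 17.

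Power at 19 per arm, with noncentrality = difference / (SD × √(2/19)) and √(2/19) = 0.3244:

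| Endpoint | Noncentrality | Normal approximation | t-test, 36 df |
|---|---|---|---|
| Eosinophils | 16.64 / (17.3 × 0.3244) = 2.965 | 84.2% | 82.2% |
| LAR | 11 / (12 × 0.3244) = 2.825 | 80.7% | 78.5% |

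The stated 80% for LAR is reproduced as a stand-alone figure.

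**Step 2: apply the sequence.** P(LAR declared) = P(eosinophil p ≤ 0.05 and LAR p ≤ 0.05). If the tests are independent, this is 0.8224 × 0.7850 = 0.6457. For an assumed correlation rho it is the bivariate normal probability that matches the two marginal t-test powers. This was checked by simulating pairs of t-tests (100,000 trials per row).

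| rho (assumed) | Bivariate normal | Simulated t-tests |
|---|---|---|
| 0 | 64.57% | 64.65% |
| 0.3 | 67.11% | 67.36% |
| 0.5 | 69.15% | 69.05% |
| 0.7 | 71.66% | 71.46% |
| 0.9 | 75.21% | not run |

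Limits for any form of dependence: at least 82.2 + 78.5 − 100 = 60.7%, and at most the smaller marginal power, 78.5%. By the normal approximation the joint figures are 68.0% (rho 0), 70.2% (0.3), 72.1% (0.5) and 74.3% (0.7), with a ceiling of 80.7%.

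**Step 3: a LAR test that is actually reached.** Conditional power = joint power / eosinophil power: 64.57 / 82.24 = 79% at rho 0, and 71.46 / 82.24 = 87% at rho 0.7.

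**Step 4: if 38 means randomised.** Assume 2 subjects per arm without Visit 11 data (4 of 38, about 10%), which leaves 17 per arm. Marginal t-test power is 77.6% (eosinophils) and 73.6% (LAR). Joint power is 57.2% at rho 0 and 65.4% at rho 0.7. The loss rate is an illustration; the protocol gives none.

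**Step 5: sensitivity to covariate adjustment.** Suppose the stated SDs are unadjusted and the screening covariate has correlation c with the outcome (assumed). The SD then shrinks by √(1 − c²). With 36 df kept for simplicity, and the tests independent:

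- c = 0.3: 85.6% × 82.2% = 70.4%.
- c = 0.5: 91.5% × 88.8% = 81.2%.

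**The case against.** The strongest reply is that nothing in section 8.2 is miscalculated. It claims power for each endpoint separately, names the step-down order in the same section and points to section 8.5. It nowhere claims 80% for the sequence, and it closes by describing an estimation-type approach. This stands in part: a reader might infer that the 80% is an arithmetic error, and it is not. What is missing is the figure that corresponds to the decision rule.

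Second, 65% to 71% is not a fixed property of the design. It needs a correlation that the protocol does not give, and it uses unadjusted t-tests although sections 8.5.1.1 and 8.5.1.2 adjust for screening covariates. This also stands. Correlation alone cannot restore 80% on the t-test, because the ceiling is 78.5%. Covariate adjustment could, but only if the SDs are unadjusted and the covariates are fairly strong, and section 8.2 says neither.

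Third, a reader might infer that a negative LAR test comes from a test with only two chances in three. The documents do not support that. LAR is tested only after the eosinophil test has succeeded, and a test then reached has about 79% to 87% power. An untested LAR is recognisable as such from the rule in section 8.5.

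Fourth, a reader might infer that the trial will fall short of 38 evaluable subjects. That is not shown. Only the synopsis ties 38 to randomisation, section 1.4 speaks of completion, and replacement is permitted. Low FEV1 does not by itself cost data, because section 4.2.2.2 allows procedures to continue at the investigator's discretion or be rescheduled.

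**Conclusion.** The point holds as a statement about the planned probability of declaring LAR. Section 8.2 gives marginal power of about 80%. Under section 8.5's rule and the plan's own inputs, the chance of declaring the 11-point difference is about 65% (rho 0) to 71% (rho 0.7), and at most 78.5% at any correlation. These figures assume unadjusted t-tests, 19 evaluable subjects per arm, true effects as stated for both endpoints, and a correlation chosen for illustration.

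The whole of that reduction comes from the test sequence; the meaning of 38 contributes nothing to it. The conflict between the synopsis and section 1.4 is a separate inconsistency. It matters because some subjects can stay in the study without primary data, and because replacement is optional. If 38 means randomised, the joint figure would fall further, for example to 57% to 65% with 17 evaluable per arm.

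**What to change.** In section 8.2, label the 80% as power for each endpoint tested alone. Add the power to reject LAR under the fixed sequence over a stated correlation range, and say whether the SDs are adjusted for the screening covariates. If the sponsor counts on a gain from adjustment, the assumed covariate correlation should be given.

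Make the synopsis, section 1.4 and section 8.2 agree on whether 38 is the number randomised or the number evaluable for both primary endpoints at Visit 11. If randomised, restate the power with an explicit loss assumption. If evaluable, say how that number will be reached, including for subjects who miss the first allergen challenge but remain in the study.

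The cost is protocol text and a less favourable printed figure. No test, alpha level or estimate changes. For orientation, if 80% were wanted for the sequence itself, independent t-tests would need about 25 evaluable per arm (81.2%; 24 per arm gives 79.0%). The fix does not require that increase.
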